### 8.3

CCI [REDACTED]  
[REDACTED]  
[REDACTED]  
[REDACTED]  
[REDACTED]

- CCI [Redacted]
- █ [Redacted]
- █ [Redacted]
- █ [Redacted]

Summary statistics will be provided by treatment groups. Statistical comparisons will be evaluated using the same MMRM model described in the primary analysis at a nominal 0.05 level (two-sided).

**8.5** CCI [Redacted]

[Redacted]

[Redacted]

[Redacted]

- █ [Redacted]
- █ [Redacted]
- █ [Redacted]
- █ [Redacted]
- █ [Redacted]
- █ [Redacted]
- █ [Redacted]
- █ [Redacted]
- █ [Redacted]
- █ [Redacted]

[Redacted]

CCI [REDACTED]  
[REDACTED]  
[REDACTED]  
[REDACTED]  
[REDACTED]

## 8.7 Actigraphy and eDiary Data

Since actigraphy and eDiary are tools to assist the CST in monitoring CMAI rater training, actigraphy and eDiary information will not be made available to site personnel, will not be included in the clinical database, and will not be statistically analyzed.

## 9 Safety Analysis

Standard safety variables to be analyzed include AEs, clinical laboratory tests, vital signs, ECGs, body weight, waist circumference and physical examination. In addition, data from the following safety scales will be evaluated: MMSE score, CCI [REDACTED]

[REDACTED]  
[REDACTED]  
[REDACTED]  
[REDACTED]  
[REDACTED]

Safety analysis will be conducted based on the Safety Sample. In general, baseline of a safety variable is defined as the last observation of the variable before taking the first dose of IMP, unless specified otherwise.

### 9.1 Adverse Events

All adverse events will be coded by primary system organ class (SOC) and Medical Dictionary for Regulatory Activities (MedDRA version 19.0 ) preferred term (PT). AEs that are gender-specific, e.g., ovarian cancer, will have their incidence rates evaluated for the specific gender. The incidence of the following events will be summarized by treatment group:

- a) Treatment-emergent AEs (TEAE) by SOC and PT
- b) TEAEs at least 5% in the brexpiprazole group and twice greater than placebo
- c) TEAEs at least 2% in the brexpiprazole group and greater than placebo
- d) TEAEs by severity

- e) Potentially drug-related TEAEs
- f) TEAEs with an outcome of death
- g) Serious TEAEs
- h) TEAEs leading to discontinuations
- i) EPS-related AEs
- j) EPS-related AEs by time
- k) AEs of special interest
- l) TEAEs by gender, race, age and region

EPS-related AEs will be grouped into five categories.

- 1) Dystonic Events, which include cervical spasm, dystonia, emprosthotonos, muscle contractions involuntary, muscle rigidity, muscle spasms, muscle spasticity, myotonia, nuchal rigidity, oculogyration, opisthotonos, pleurothotonus, risus sardonicus, torticollis, and trismus;
- 2) Parkinsonian Events, which include akinesia, asterixis, athetosis, bradykinesia, cogwheel rigidity, essential tremor, extrapyramidal disorder, freezing phenomenon, gait festinating, hypertonia, hypokinesia, hypokinesia neonatal, intention tremor, masked facies, parkinson's disease, parkinsonian crisis, parkinsonian gait, parkinsonian rest tremor, parkinsonism, tremor, and tremor neonatal;
- 3) Akathisia Events, which include akathisia, hyperkinesia, and psychomotor hyperactivity;
- 4) Dyskinetic Events, which include ballismus, buccoglossal syndrome, choreoathetosis, clumsiness, dyskinesia, dyskinesia neonatal, dyskinesia oesophageal, fumbling, nodding of head, on and off phenomenon, and tardive dyskinesia;
- 5) Residual Events, which include chorea, huntington's chorea, muscle twitching, and myoclonus.

CCI  
[Redacted text block]

The following AEs of special interest will be summarized by PT terms only:

- 1) Fall
- 2) Orthostatic hypotension
- 3) Syncope
- 4) Dizziness

Treatment-emergent AEs are defined as AEs with an onset date on or after the start of double-blind treatment. In more detail, TEAEs are all adverse events which started after

start of double blind study drug treatment; or if the event was continuous from baseline and was worsening, serious, study drug related, or resulted in death, discontinuation, interruption or reduction of study therapy. Adverse Events occurring up to 30 days after the last day of double-blind dosing will be included in the summary tables.

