### 1.3. Known and Potential Risks and Benefits

Based on the Investigator's Brochure, combined data from the completed phase 1 clinical trials indicate that brexpiprazole is safe and well tolerated in healthy subjects at single oral doses of 0.2 to 6 mg and at multiple oral doses up to 2 mg/day. Data from the completed multiple-dose clinical trials indicate brexpiprazole is well tolerated at multiple oral doses up to 12 mg/day in subjects with schizophrenia or schizoaffective disorder; up to 4 mg/day when coadministered with marketed ADT in subjects with MDD; and up to 4 mg/day when coadministered with marketed stimulant therapy in subjects with ADHD.

Based on data from the 18 completed phase 1 clinical trials in healthy subjects or special populations (including healthy subjects from 2 phase 1 trials conducted in special populations) (15 in the US, 2 in Japan, and 1 in Korea), the most frequently reported TEAEs (incidence  $\geq$  5% or more of all healthy subjects who received brexpiprazole and more than placebo, administered either alone or with another marketed drug) were:

- Healthy subjects (N = 15 trials conducted in the US): dizziness, headache, postural dizziness, nausea, somnolence, constipation, and diarrhoea
- Healthy subjects (N = 3 trials conducted in Japan and Korea): nausea, orthostatic hypotension, somnolence, and dizziness

By indication, the most frequently reported TEAEs (incidence  $\geq$  5% or more of all subjects who received brexpiprazole and more than placebo, administered either alone or with another marketed therapy or drug (ie, ADT, stimulant therapy, or antibiotic) in completed phase 1, phase 1b, and/or phase 2 double-blind patient trials (excluding subjects enrolled in phase 2 open-label extension trials) conducted under US Investigation New Drug Applications (INDs) were:

- Schizophrenia or schizoaffective disorder (N = 4 trials): headache, anxiety, akathisia, nausea, increased weight, and dizziness

Protocol 331-12-284

- MDD (N = 3 trials): akathisia, increased weight, insomnia, upper respiratory tract infection, and nasopharyngitis
- ADHD (N = 2 trials): insomnia

In the single completed phase 1 trial in subjects with schizophrenia conducted in Japan, TEAEs reported in 3 or more subjects who received brexpiprazole (of 21 total subjects) were:

- Schizophrenia (N = 1 trial): increased serum prolactin and increased serum creatine phosphokinase

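### The special-interest adverse event summary has no row for postural dizziness, and no visible table counts subjects with any orthostatic-type event once per arm

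*SAP*

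**What the plan says.** SAP 9.1 codes adverse events to MedDRA 19.0 preferred terms and lists the summaries to be produced by treatment group. These include "Treatment-emergent AEs (TEAE) by SOC and PT", a table of events reaching 5% on brexpiprazole at twice the placebo rate, a table of events reaching 2% and exceeding placebo, and a special-interest summary. The special-interest summary is introduced by "The following AEs of special interest will be summarized by PT terms only". Four terms follow: Fall, Orthostatic hypotension, Syncope and Dizziness. A redacted block stands directly before that sentence.

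Protocol 1.3 summarises earlier experience. For the US phase 1 trials it lists "Healthy subjects (N = 15 trials conducted in the US): dizziness, headache, postural dizziness, nausea, somnolence, constipation, and diarrhoea", having set the criterion as an incidence of "5% or more of all healthy subjects who received brexpiprazole and more than placebo". Dizziness and postural dizziness are separate entries in that one list.

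For vital signs, SAP 9.3 and SAP Appendix 2 provide an incidence by treatment group of potentially clinically relevant values, with an explicit orthostatic hypotension criterion. The protocol's Schedule of Assessments takes supine, sitting and standing readings at every clinic visit from screening to Week 12/ET.

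**The concern.** Orthostatic hypotension, syncope and dizziness are related in a clinically obvious way, and a fall is a common consequence. Postural dizziness is the symptom closest to orthostatic hypotension, yet it is the one related term that the protocol names and the list omits.

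Subjects are 55 to 90 years old and have dementia. Protocol 1.1.2 attributes the blood pressure decrease seen in animals to alpha-1 adrenoceptor blockade, and Protocol 1.3 lists orthostatic hypotension among the frequent events in healthy subjects in Japan and Korea. A reader looking for this kind of harm would go first to the special-interest summary. There, subjects whose only related event is postural dizziness would not appear. Nor could the reader work out from separate preferred-term rows how many subjects in each arm had at least one such event.

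**Working it through.** The point concerns which terms a table counts, so the main check is to set the lists side by side.

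| Source | Dizziness | Postural dizziness | Orthostatic hypotension |
|---|---|---|---|
| SAP 9.1 special-interest list (visible text) | yes | no | yes |
| Protocol 1.3, healthy subjects, US trials | yes | yes | no |
| Protocol 1.3, healthy subjects, Japan and Korea | yes | no | yes |
| Protocol 1.3, schizophrenia | yes | no | no |
| Protocol 1.3, MDD | no | no | no |
| Protocol 1.3, ADHD | no | no | no |

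The schizophrenia entry reads "headache, anxiety, akathisia, nausea, increased weight, and dizziness".

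1. *Does postural dizziness match a row?* The special-interest rule works on preferred terms. The protocol reports dizziness and postural dizziness as two entries in one list, so the sponsor's own reporting keeps them apart. If MedDRA 19.0 coding in this trial does the same, an event coded to postural dizziness enters none of the four rows.

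2. *Where would it appear instead?* It appears by arm in the table by system organ class and preferred term, whatever its frequency. For the threshold tables, take the planned 130 subjects per arm as the denominator. Then 0.02 × 130 = 2.6, so at least 3 brexpiprazole subjects are needed for the 2% table; 0.05 × 130 = 6.5, so at least 7 are needed for the 5% table. The placebo comparison must be met as well. A term reported by 1 or 2 brexpiprazole subjects would stay only in the full table.

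3. *Can the reader rebuild the combined count?* Let n₁ to n₄ be the subjects in one arm with orthostatic hypotension, dizziness, postural dizziness and syncope. The number with at least one of them lies between the largest of the four and the smaller of n₁ + n₂ + n₃ + n₄ and the arm size. Because one subject can report several terms, summary rows alone do not fix it. The visible text specifies no table that does.

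4. *Is pooling foreign to this plan?* No. The same section groups extrapyramidal events from many preferred terms into five categories.

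**The case against.** The strongest reply is that nothing goes unreported. A reader might infer from the four-term list that postural dizziness drops out of the safety report. The documents do not support that: the event is tabulated by arm in the full preferred-term table, in the threshold tables when it qualifies, and where applicable in the severity, drug-related, serious, discontinuation and subgroup tables. This part of the reply stands in full.

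The second reply is that orthostatic hypotension is measured directly. That also stands, and it does not depend on symptom reporting. It is only a partial substitute, because the criterion in SAP Appendix 2 requires both a systolic fall of at least 20 mmHg and a heart rate rise of at least 25 bpm. Symptoms without both changes at a visit are recorded only as adverse events.

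Third, a reader might take postural dizziness to be a frequent event with this drug in general. Protocol 1.3 does not say so. It appears only in the US healthy-subject list, where brexpiprazole was given alone or with another marketed drug. It is absent from the Japan and Korea healthy-subject list and from the patient-trial lists. Protocol 1.1.2 adds that the cardiovascular changes in animals generally occurred above the exposures giving efficacy in rats. Protocol 1.3 reports no consistent, clinically relevant blood pressure or heart rate changes in completed phase 1 and 2 trials in MDD or schizophrenia.

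Fourth, the SAP does not state that its list represents an orthostatic concept, and current Protocol 7.6.1 requires no special-interest table. Grouping is therefore an improvement to the plan; its absence contradicts nothing.

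Finally, the redacted block could contain further groupings, so the absence of a combined category can be asserted only for the visible text.

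**Conclusion.** The point holds as a minor one. On the visible text of SAP 9.1, an event coded to postural dizziness falls in none of the four special-interest rows, and no visible table gives the number of subjects per arm with any of the related events. The concept is split across terms; the events themselves remain in the report.

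The size cannot be stated. The documents give no rate of postural dizziness in an elderly or dementia population, and any figure would be invented. The special-interest summary has no stated test or decision rule attached, so the efficacy conclusions, type I error and sample size are unaffected. What changes is how easily a safety reader can compare the arms on a plausible harm.

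The conclusion assumes that coding in this trial keeps postural dizziness separate from dizziness, as the protocol's list does, and that the redacted block holds no grouping that already covers these terms. If it does hold one, the sponsor can close the combined-row part by pointing to it; the visible term-only list would still omit this term. Severity is low.

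**What to change.** Before unblinding, make two additions to SAP 9.1:

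- Add the MedDRA 19.0 preferred term for postural dizziness to the special-interest list.
- Add one combined row by treatment group for orthostatic hypotension, dizziness, postural dizziness or syncope, with each subject counted once. Fall keeps its own row.

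The cost is one term and one table row, programmed from adverse event data already collected and coded. No new assessment, protocol change or adjustment to alpha or sample size is needed. Fixing the grouping before treatment codes are known also protects it from the charge that terms were chosen after seeing the results.

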## 2. Trial Rationale and Objectives

### 2.1. Trial Rationale

Behavioral symptoms, such as agitation, are core features in subjects with Alzheimer's disease and related dementias and develop in the majority of dementia subjects. The presence of agitation in subjects with Alzheimer's disease places a significant burden not only on subjects and their caregivers but also on the healthcare system.

Based on the data available from atypical antipsychotics in the treatment of agitation or aggression in Alzheimer's disease, brexpiprazole is an appropriate candidate to evaluate the benefit-risk ratio of this class of drugs in this subject population in today's clinical setting. In addition to potential treatment effects, the receptor binding profile of brexpiprazole may confer additional benefits in terms of the safety profile, particularly with respect to hyperprolactinemia, sleep quality, and weight gain.

In light of the Food and Drug Administration (FDA) boxed warning of increased mortality with the use of antipsychotics in elderly subjects with dementia-related psychosis and similar caution advised by other regulatory authorities, the clinical trial will be conducted in an environment that allows for close safety monitoring, in subjects who are living in either an institutionalized setting or in a non-institutionalized setting where the subject is not living alone and has a caregiver who can spend a minimum of 2 hours per day for 4 days per week with the subject in order to assess changes in the subject's condition. Furthermore, a slow titration schedule will be implemented with brexpiprazole being titrated to the highest assigned dose (2 mg/day) over a 4-week period. CCI

[REDACTED]

[REDACTED]

[REDACTED]

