cd All subjects, whether they complete the trial or are withdrawn prematurely for any reason, will be followed up for a safety evaluation ~~at 30 (+ 2) days after the last dose of IMP during~~ a clinic visit at *either* the *investigator's site or* residential facility ~~30 (+ 2) days after the last dose of IMP~~. If the *institutionalized* subject has left the residential facility where he or she participated in the trial, the subject should be seen ~~at~~ *in* the investigator's site, clinic or (if a clinic visit is not possible), the subject should be assessed by telephone contact with the subject and a caregiver. Subjects who complete both the 12-week double-blind treatment period and the 30-day safety follow-up visit are eligible to enroll into Trial 331-13-211, which is a 2-month, observational, rollover trial to evaluate the safety of subjects with agitation associated with Alzheimer's disease who previously participated in Trial 331-12-283. For those subjects who plan to enroll into Trial 331-~~132~~-211, the 30-day safety follow-up visit for Trial 331-12-283 will occur as a clinic visit at *either* the *investigator's site or* residential facility. If the *institutionalized* subject has left the residential facility where he or she participated in the trial, the 30-day safety follow-up visit will occur as a clinic visit at the investigator's site.

d Note that this visit is 16 weeks postbaseline.

k After the ICF is signed during the screening visit, the actigraphy device will be put on the subject's nondominant wrist and worn daily until Week 12/ET. *It is recommended that the Actigraph must* be checked daily to ensure that the subject is wearing it and that it continues to be operational.

Protocol 331-12-284

PSubjects **should must** be fasting for a minimum of 8 hours prior to blood draws for screening laboratory assessments, if at all possible. If fasting blood samples are not feasible at screening, nonfasting blood samples may be obtained initially for determining eligibility for the trial.

...

VCCI

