## **3 Trial Design**

This is a phase 3, 12-week, multicenter, randomized, double-blind, placebo-controlled, 2-arm, flexible-dose trial designed to assess the efficacy, safety, and tolerability of brexpiprazole (dose range of 0.5 mg/day to 2 mg/day) in the treatment of subjects with agitation associated with dementia of the Alzheimer's type. The trial population will include male and female subjects between 55 and 90 years of age (inclusive), who are living in either an institutionalized setting (e.g., nursing home, dementia unit, assisted living facility, or any other residential care facility providing long term care) or in a non-institutionalized setting where the subject is not living alone. In both the institutionalized and non-institutionalized settings, the subject must have a caregiver who can spend a minimum of 2 hours per day for 4 days per week with the subject in order to assess changes in the subject's condition. All subjects must have a diagnosis of probable Alzheimer's disease according to the National Institute of Neurological and Communicative Disorders and Stroke and the Alzheimer's Disease and Related Disorders Association (NINCDS-ADRDA) criteria.

The trial comprises a 2- to 42-day screening period, a 12-week double-blind treatment period, and a 30-day post-treatment follow-up period. In addition, for all subjects who terminate early from the study, all attempts will be made to collect mortality data by telephone contact with the subject's caregiver at Week 16.

This trial will be monitored under the supervision of an independent Data Monitoring Committee (DMC). The DMC will monitor safety periodically, based on a predetermined schedule. The details of the DMC structure and its roles and responsibilities will be documented in a DMC charter.

The trial is organized as follows:

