#### *Follow-up Period*

All subjects, whether they complete the trial or are withdrawn prematurely for any reason, will be followed up for a safety evaluation 30 (+ 2) days after the last dose of the IMP during a clinic visit at either the investigator's site or residential facility, if applicable. If a clinic visit is not possible, the subject should be assessed by telephone contact with the subject and a caregiver. For all subjects who terminate early from the study, all attempts will be made to collect mortality data by telephone contact with the subject's caregiver at Week 16.

Subjects who complete both the 12-week double-blind treatment period and the 30-day safety follow-up visit are eligible to enroll into Trial 331-13-211, which is a 2-month, observational, rollover trial to evaluate the safety of subjects with agitation associated with Alzheimer's disease who previously participated in Trial 331-12-284. For those subjects who plan to enroll into Trial 331-13-211, the 30-day safety follow-up visit for Trial 331-12-284 will occur as a clinic visit at either the investigator's site or residential facility, if applicable.

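### On the visible text, the SAP's 30-day limit on AE tables has no exception for deaths, so part of the Week 16 mortality follow-up in early terminators lies outside the only visible table naming death

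*SAP*

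**What the plan says.** SAP 3 (Trial Design) states that "for all subjects who terminate early from the study, all attempts will be made to collect mortality data by telephone contact" with the caregiver at Week 16, and repeats this under Follow-up Period. The call does not depend on when dosing stopped.

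SAP 9.1 lists the AE summaries. The only visible entry that names death is "f) TEAEs with an outcome of death", and Protocol 7.6.1 has the same item. Serious TEAEs (item g) would also contain deaths, but they fall under the same rule. The visible events of special interest are fall, orthostatic hypotension, syncope and dizziness.

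On timing, SAP 9.1 says "Treatment-emergent AEs are defined as AEs with an onset date on or after the start of double-blind treatment", which sets a start but no end. The end comes from the last sentence of the section: "Adverse Events occurring up to 30 days after the last day of double-blind dosing will be included in the summary tables". Death is mentioned just before that sentence, but only as one reason for counting an event already present at baseline as treatment-emergent. It does not extend the 30 days.

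**The concern.** Protocol 2.1 gives the "boxed warning of increased mortality with the use of antipsychotics in elderly subjects with dementia-related psychosis" as a reason for close safety monitoring, so deaths are a safety outcome that the trial itself puts forward. The plan collects them to a fixed point after baseline, but the visible table closes at a point that depends on when each subject stopped dosing. Completers are covered for the whole period. Early terminators, the group for whom the call exists, are not.

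Stopping is a post-randomization event and can be related to health: Protocol 3.8.3 requires withdrawal for AEs that warrant it, for intolerance of the lowest maintenance dose, and for unsafe agitation that cannot be adequately treated. A death window tied to last dose could therefore differ in length between arms. With 260 subjects and probably few deaths, one omitted death could alter how the comparison reads.

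**Working it through.** The plan states no figure for this mismatch, so there is nothing to reproduce. The check is calendar arithmetic.

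**Inputs**
- Day 1 is the first dose, the day after the baseline visit on Day 0 (Protocol 3.2; SAP 10.1).
- Planned treatment is 12 weeks, or 84 days (SAP 3).
- AE tables close 30 days after last dose (SAP 9.1).
- The call is at Week 16. The Amendment 2 log in Protocol Appendix 22 says "Note that this visit is 16 weeks postbaseline", giving 16 × 7 = Day 112. The current footnote is redacted, so the log is used only to fix this date.

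**Formula.** For last dose on Day L, the table closes on Day L + 30. Follow-up outside it is max(0, 112 − (L + 30)) = max(0, 82 − L) days. The last column divides this by the days from last dose to the call, 112 − L.

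| Last dose (Day L) | Table closes | Days outside table | Share of days after last dose |
|---|---|---|---|
| 1 | 31 | 81 | 81/111 = 73% |
| 14 | 44 | 68 | 68/98 = 69% |
| 28 | 58 | 54 | 54/84 = 64% |
| 42 | 72 | 40 | 40/70 = 57% |
| 56 | 86 | 26 | 26/56 = 46% |
| 70 | 100 | 12 | 12/42 = 29% |
| 82 | 112 | 0 | 0 |
| 84 (completer) | 114 | 0 | 0 |

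If stops were spread evenly over Days 1 to 83 (an assumption), the mean would be (81 + 80 + … + 1)/83 = 3321/83 = 40.0 days.

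**Which deaths are affected.** The rule speaks of when the adverse event occurs. If that means onset, a death after the window from an event that began inside it stays in the table. What can drop out is a death from an event starting more than 30 days after last dose, or one known only from the call with no AE record. The second route is possible because Protocol 5.7.3 asks for new SAEs after the last scheduled contact only when judged reasonably associated with IMP. If occurrence means the date of death, every death after the window is affected. The SAP does not say which is meant.

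**Illustrative count.** The documents give neither an early-termination rate nor a mortality rate. Suppose 10% to 30% of 260 subjects stop early, all at Day 42, with mortality of 5% to 15% per year. Expected deaths in the gap, both arms together, then run from 260 × 0.10 × (40/365.25) × 0.05 = 0.14 to 260 × 0.30 × (40/365.25) × 0.15 = 1.28. These are ceilings under those assumptions, since on the onset reading some of these deaths would still be tabulated.

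**The case against.** **A mortality table may already exist.** A reader might infer that the plan never analyses the Week 16 data. The documents do not support that. SAP 9.1 has a blacked-out block, SAP 9.6 and 9.8 and Protocol 7.6.5 and 7.7 are redacted, the protocol's current mortality text is largely redacted, and the contents of the SAP 13 table list could not be seen. This objection stands. The point is confined to the visible rule, and a cross-reference would answer it if the table exists.

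**The sentence includes; it does not exclude.** It says which events go in, not that later ones stay out, and the TEAE definition has no upper limit. Literally this is right. Still, the sentence would serve no purpose if later events were also tabulated, so exclusion is the natural, though implied, reading.

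**Not every late death is lost.** A reader might take every death beyond 30 days to be uncounted. On the onset reading that is too broad. The day counts measure follow-up outside the table, not deaths lost.

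**Bias is not shown.** A reader might conclude that the rule favours the arm with more withdrawals. No document gives termination or mortality by arm, or shows that early stoppers carry more risk after 30 days. Unequal windows are possible; their direction and effect are not established.

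**Thirty days is a reasonable on-treatment window.** It matches the planned safety follow-up. This stands, and the existing table should be kept.

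**Conclusion.** The point holds as a mismatch in the visible text. Mortality is sought to Week 16 for all early terminators, but the only visible table naming death follows a limit of 30 days after last dose with no exception for deaths. Up to 82 − L days of collected follow-up fall outside it for a last dose before about Day 82, and none for completers.

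This rests on taking Week 16 as Day 112 from the Amendment 2 log, on reading the sentence as a limit, and on no separate summary sitting in unseen text. The documents do not give the size or direction of any difference between arms, and the number of deaths affected may be zero. The correction is worth making because it is cheap and removes a window that depends on post-randomization events from an outcome the protocol singles out.

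**What to change.** In SAP 9.1:

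1. Exempt deaths from the 30-day limit.
2. Add one table and one listing of all-cause deaths by randomized arm in the Safety Sample, from first dose through the Week 16 contact. Include deaths learned only from the call, days since last dose, and the number with unknown vital status. If such a summary already exists in redacted text, a cross-reference beside the 30-day sentence is enough.
3. Keep the 30-day table of fatal TEAEs as the on-treatment view.
4. State whether *occurring* refers to AE onset date or death date.

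A Kaplan-Meier display is optional and adds little if deaths are few.

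The cost is one sentence, one table and one listing. The plan already provides for collecting the data. The reported number of deaths may be higher.
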